In line with Secondary Aim 1, overweight sibling height and weight will also be assessed at each major assessment time point in the same manner described above. *Alternatively, parents also have the option to give consent for assessors to review the non-participating sibling(s)'s medical records to access height and weight data (DSMB approved protocol addenda, 11.2.18)*. Additionally, non-participating parent and other sibling heights and weights will be assessed at each major assessment time point if feasible.

Delay discounting will be assessed at baseline and again at 12 and 24 months through use of a brief computer task administered via REDCap on a laptop. Additionally, baseline predictors of treatment outcome will be assessed, specifically, parental inconsistency in rewards and environmental enrichment of the home. Data will be collected using self-report questionnaires designed to assess these constructs administered on-line via REDCap (see **Appendix C**). Finally, for the FBT group, treatment adherence will be measured throughout the study by treatment session attendance and completion of diet and physical activity self-monitoring in habit books or specialized mobile applications.

Participant Timeline

1. Enrollment/Baseline

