Participants will be tracked in REDCap in order to maximize retention in the study and, as necessary, to capture any drop-outs or withdrawals that occur during the study period. PLAN coaches can verify the status of their FBT families by accessing the REDCap Record Status Dashboard, which will list all existing records/responses and their status (i.e., incomplete or complete) for every data collection instrument in the study. PLAN coaches can verify that FBT families and UC families at their site have completed assessment time points as well as the family members that participated in these assessments. Additionally, PLAN coaches can utilize the REDCap calendar to manage participants and appointments, and they will complete Tracking Forms each week to document session attendance or absence of their FBT families. In order to ensure that families in both arms are captured at all necessary time points, the DCC will send regular reports to indicate participant status and subsequent required actions on behalf of the study team.

5. Participant Withdrawal or Termination

Children and parents can withdraw from the research at any time, and siblings and non-participating parents can withdraw or be withdrawn without any consequences to the other family members’ status in the study. If participants withdraw, they will be debriefed about the nature of the study, asked permission to obtain data collection through medical records or brief appointments, and, if terminated, provided with the reason for their removal as well as a referral if deemed appropriate. Any information that had been provided may be retained by the researcher and analyzed. This includes permission to collect body composition information from their physicians at determined measurement time points (if not revoked upon their withdrawal).

Participants who exhibit unhealthy weight loss, clinically concerning symptoms of disordered eating, or develop an illness or condition that would bias the data may be withdrawn from research analyses, as determined by the SEC, SMC, and the Data Safety and Monitoring board (see **section IX**) and referred to an appropriate professional (*This change was made on 3.23.18 prior to review and approval by the DSMB, DSMB approved protocol addenda on 11.2.18*).

Lost to Follow-Up for FBT Families (DSMB approved protocol addenda, 9.29.19): A designation of Lost to Follow-Up (LTF) is applied to intervention families that we have not had contact with for 3 months (90 Days).

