Standard features of REDCap and automated procedures of the Division of Biostatistics provide a high degree of certainty that subject confidentiality will be maintained and that data will never be lost. In accordance with the two key HIPAA requirements, password protection will be required for access to study computers and REDCap. Only authorized personnel will have access to the data entry system and access will be restricted to data from one's own clinic. Data entered into REDCap are encrypted when transferred to SAS. Standard security and confidentiality measures at the DCC include requiring that employees sign confidentiality agreements, that personal identifiers are included in electronic databases only under strong necessity, and that encryption is used when identifiers are present in SAS datasets. Access to our Division computers is restricted to our faculty, staff, and collaborators. Access to accounts that store data from this study will be restricted to DCC personnel and the division's network manager. All file transfers to outside computers use secure transfer methods which ensure that all such traffic is encrypted. The entire network wiring plant within the Division is behind a firewall and is contained within space physically controlled by us. Access to all computers and to REDCap is automatically logged.

Forms and Datasets Manual

All data entered into REDCap will be transferred to SAS using automated procedures for use in future data analyses and reports. Each dataset in the database will contain labels and formats. To facilitate use of this database, the DCC will prepare and maintain a detailed "Forms and Datasets Manual", an easy-to-use roadmap for finding the dataset where a particular data item is stored. The key component of the manual will be a codebook which contains an alphabetical list of all variable names in the entire database, with associated labels and formats for each variable. The codebook will also contain the name of the dataset in which each variable is stored. In addition to the codebook, the Forms and Datasets Manual will include detailed contents of each dataset, a

comprehensive set of data forms with variable names next to each entry, and a format library. We routinely use such manuals in large studies for a variety of reasons, the most important being that they greatly facilitate data management and analysis by making it very easy to find where in a large database an item on a particular form is stored.

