know the intervention arm by the very nature of implementing a behavioral intervention. Pediatricians will not be told group assignment, but that is possible to discern since they may see FBT families coming to their clinic more than the UC families.

Masking of Assessment Staff

We recognize the importance of blinding research personnel who are collecting data to study arms. The primary height and weight data will be collected coaches conduct assessments for each other's families at the different pediatric sites (for which they will be blinded to those families). Families will be explained that they are to not discuss anything regarding their group assignment, how often they come to the pediatric office or their coaches and the measurement assessor has to remain blinded to their treatment arm.

Coaches will be blinded to the families' randomization. They will conduct assessments, home visits, remote assessments, and AE data collection.

There are three coaches at each site, with *some sites having backup and floating coaches that are involved in delivering FBT to study participants. A backup coach delivers treatment for another coach's caseload in the event that a coach goes on vacation, leaves the position, or is otherwise unable to complete treatment with their families. Backup coaches are assigned based on coach letter assignment (i.e., coach B is the backup for coach A, coach A is the backup for coach C, coach C is the backup for coach B). This ensures that there is always a blinded measurement coach to complete assessments. A floating coach delivers treatment to families at multiple pediatric practices regardless of coach assignment. Floating coaches remain blinded to other caseloads, but see families at different practices when a practice's coach does not have space in their caseload for more families (This change was made on 12.4.18 prior to review and approval by the DSMB, DSMB approved protocol addenda on 11.18.19).* The plan is for Coach 1 to collect height and weight for families assigned to Coach 2, Coach 2 will collect height and weight for families assigned to Coach 3, and Coach 3 will collect height and weight for families assigned to Coach 1. Thus, coaches will not collect height and weight measures from families from their caseload. We will use block scheduling to reduce travel time (e.g., Coach 1 can do assessments at Coach 2's site one Friday per month).

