In order to mask assessment of outcome measures,-all sites have implemented blinded measurement coaches that complete assessments and AE data collection, so that the PLAN coaches can focus on treatment. Coaches will remain blinded to group assignment outside of their caseload (This change was made on 2.28.18 prior to review and approval by the DSMB, DSMB approved protocol addenda on 11.2.18). To further ensure blinding, families will be notified that the assessor is unaware of their group assignment and will be asked not to discuss the frequency of them coming in to the practice, their group assignment, or the coach they normally see (DSMB approved protocol addenda, 3.18.19).

Although not possible to guarantee that coaches are blind to condition for families that are not in their caseload due to the families not being blinded, use of a standard protocol (see **Appendix C**) ensures objective and reliable measurement of the primary outcome. Assessors will be blind to prior heights/weights, further protecting against assessment bias.

Reducing Bias in Unmasked Groups

We recognize that there are numerous ways that the PLAN coaches or pediatricians can treat FBT UC families differently. We have several approaches to reduce bias. We are able to standardize interactions with PLAN coaches through extensive training, supervision and fidelity checks, which can help reduce bias from the PLAN coaches. Part of the training will include instructions not to state or imply that FBT may be better than usual care. We will not be directly training or assessing fidelity for usual care, as that would deviate from the reason for using UC as the control condition. However, we will be collecting information on usual care practices from participating providers at baseline and 24 months via REDCap surveys. Group assignment will not be in the families' charts, and unless a family directly says something to the pediatrician, the pediatrician may be unaware of group assignment.

II. Study Administration

Study Website

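### REDCap access for PLAN coaches, as written, leaves assessor blinding to arm and to earlier measurements unprotected, and should be limited by role

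*Combined protocol and SAP*

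**What the plan says.** **Access.** Participant Retention, item 4 (Participant Tracking) gives coaches a status dashboard within REDCap, "which will list all existing records/responses and their status (i.e., incomplete or complete) for every data collection instrument in the study". It introduces the dashboard as a way for coaches to follow their own FBT families. The next sentence is wider: "PLAN coaches can verify that FBT families and UC families at their site have completed assessment time points". Data Security and Confidentiality states the only limit on who sees what: "access will be restricted to data from one's own clinic".

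**Who measures.** Masking of Assessment Staff sets out a rotation among the coaches at a site: "The plan is for Coach 1 to collect height and weight for families assigned to Coach 2", and so on round the three. The same section later says that every site now has blinded measurement coaches who do the assessments.

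**What the assessor must not know.** That section requires two things: "Coaches will remain blinded to group assignment outside of their caseload", and "Assessors will be blind to prior heights/weights, further protecting against assessment bias".

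**How the measurement is entered.** In Appendix C, the height procedure has the measuring coach choose the family's screening ID in REDCap, arrive at that family's record home page, and open the appropriate height and weight form from there. Repeat readings are kept in REDCap for later review.

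**The concern.** Families and treating coaches cannot be masked in this trial. Blinding of the person who takes the height and weight is therefore the main protection for the primary outcome. Height matters most, because the procedure involves lifting the child's head by hand before the reading is taken. An assessor who knows the arm, or knows the last height, can lean one way without intending to.

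The plan accepts that families may let the arm slip, and that cannot be fully prevented. Database access can be controlled. The text describes access for coaches that is not limited by role, caseload or instrument, and it describes those same coaches as outcome assessors for each other's families.

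**Working it through.** The plan gives no figure on this point to reproduce, so the check sets its sections side by side. A scale calculation follows.

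1. **Is the person with access also the assessor?** Under the rotation, yes: a treating coach measures a colleague's families. Under the later sentence about dedicated measurement coaches, not necessarily. The two texts stand together and are not reconciled.

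2. **Does the assessor need to open the family's record?** Yes. The height procedure routes data entry through the record home page, so the exposure does not depend on the dashboard alone.

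3. **Would anything there show the arm?** Participant Tracking says of coaches that "they will complete Tracking Forms each week to document session attendance or absence of their FBT families". The Assessments section says that "for the FBT group, treatment adherence will be measured throughout the study by treatment session attendance". No counterpart is described for UC families. If another coach's session forms, or their completion status, can be seen by the assessor, a completed one shows the arm. Completion of assessment visits alone does not, because both arms are assessed at months 0, 6, 12, 18 and 24.

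4. **Would anything there show earlier measurements?** The coach picks the appropriate height and weight form from the family's record, which implies that forms for other visits sit in the same record. No restriction on opening them is stated.

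5. **Does the clinic limit close the route?** The word is used in two senses. In Implementation of the Intention-to-Treat Principle a clinic is a pediatric practice within a site, while under Site Visits it reads as a study site. A practice-level limit narrows the exposure. It cannot exclude the families a coach measures, because the coach must enter their data.

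**Scale (illustration only).** Percent over BMI is P = 100 × (BMI / B50 − 1), where B50 is the median BMI for age and sex. If true height h is read as h + 0.3 cm, BMI is multiplied by (h / (h + 0.3))². The 3 mm is the plan's own certification tolerance (Assessment Training and Fidelity, Certification). The child sizes are assumptions; the documents give none.

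| Height (cm) | BMI | B50 | 100 + P | Multiplier | Shift in P |
|---|---|---|---|---|---|
| 120 | 20 | 15.5 | 129.0 | (120/120.3)² = 0.9950 | −0.64 |
| 140 | 25 | 16.6 | 150.6 | (140/140.3)² = 0.9957 | −0.64 |
| 150 | 30 | 17.5 | 171.4 | (150/150.3)² = 0.9960 | −0.68 |

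Against 5.3, the smallest difference in the power table, this is 0.64/5.3 = 12% to 0.68/5.3 = 13%. It applies only if every FBT child were over-read by 3 mm and no UC child were.

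**The case against.** The tempting stronger reading is that one look at REDCap tells the assessor the arm, so that blinding of the primary outcome is defeated. The documents do not support that, for these reasons.

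- The dashboard is introduced for a coach's own FBT families. The site-wide sentence covers only assessment completion and which family members took part, and neither shows the arm. Nowhere is it said that the allocation, or another coach's session forms, are displayed to the person measuring.
- Silence on user rights is not proof that none were set. Adverse Event Assessment and Tracking keeps blinded coaches unaware of events reported between visits, which implies some separation of information by role. Operational detail is delegated to the Manual of Procedures, which is not among the documents.
- The plan says that all sites have dedicated blinded measurement coaches, and the remote protocol separates the PLAN coach from the measurement coach.
- Heights follow a standard procedure, with certification, repeat readings within 0.3 cm and calibration at each use.
- At remote visits a parent positions the child and marks the height, so REDCap rights matter less there. On planned accrual, only 56 + 84 = 140 of 528 families enrolled by March 2018 and so reached month 24 by March 2020, when in-person work was halted.

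Most of this stands, and it limits the point to an unprotected route. It does not remove the point. The rotation is still in the text. Dedicated measurement coaches also enter data in REDCap and are given no stated restricted view. Agreement between two readings by the same person limits random error but does not detect a consistent lean. The plan does concede that coach blinding cannot be guaranteed, but the reason it gives is that families are unblinded. Database access is a different and controllable route.

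**Conclusion.** The point holds in a limited form. The access described under Participant Tracking, the coach rotation and the data-entry route together leave two requirements unprotected: blinding to arm, and blinding to earlier heights and weights. This is an avoidable route to unblinding. It is not evidence that blinding failed, and a reader should not infer that it did.

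The conclusion rests on the text as supplied. If the Manual of Procedures already sets role-limited rights, what remains is to say so in the protocol and to remove the conflicting sentences.

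The size of any bias cannot be estimated from the documents. The only scale available is the illustration of 0.6 to 0.7 points, which is modest beside 5.3 and rests on assumed child sizes and a uniform one-directional error. The change is worth making because it is cheap and protects the primary outcome.

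**What to change.** 1. State REDCap user rights by role. Anyone measuring a family sees only that visit's assessment forms, with no access to session tracking, allocation, earlier heights and weights, or the status of instruments used only in FBT.
2. Limit each coach's dashboard to the coach's own caseload. For other families, use the regular participant-status reports that Participant Tracking already has the DCC sending.
3. Reconcile the two accounts in Masking of Assessment Staff: state whether treating coaches in rotation, dedicated measurement coaches, or both take the measurements, and from what date. Say whether 'clinic' in Data Security and Confidentiality means practice or site.
4. If visits have already taken place under the wider access, review the REDCap logs, as far as they record viewing, for assessors opening session or earlier measurement forms. Report what is found.

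**Cost.** Items 1 and 2 are a change to user rights, and item 3 is an edit. The real loss is that coaches give up a live site-wide view that helps retention in both arms. Periodic DCC reports largely cover it, but less promptly, so their frequency may need to rise around assessment windows.
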